Study Protocol and Statistical Analysis Plan

Study of Cerebral Structural and Functional Reorganization of Stroke Patients After Repetitive Transcranial Magnetic Stimulation (rTMS) Using the Method of Neuroimaging Brain Network Analysis

NCT Number: 03163758

Date:2013-1-1

[name]

Peking Union Medical College

[name]

Email: [contact]

Background: Many methods have been applied to facilitate recovery after stroke. However, improvement in rehabilitation strategies is necessary because many patients remain disabled after treatment^{1, 2}. Traditional methods, such as physical therapy and occupational therapy, are time-consuming and labor-intensive. Repetitive transcranial magnetic stimulation (rTMS) has been increasingly used for the treatment of depression, motor dysfunction after stroke, aphasia, and mental disorders since 2000^{3,91}. It is particularly popular in research studies on functional recovery and brain reorganization after stroke. Currently, the internationally recognized strategy is high-frequency (≥ 5 Hz) rTMS applied to the ipsilesional primary motor cortex (M1) to facilitate its reperfusion and reorganization¹⁰⁰. It has been proven to play a positive role in functional rehabilitation after stroke, and brain reorganization has been noted on functional magnetic resonance imaging (fMRI)^{9, 111}. However, low-frequency rTMS applied to the contralesional M1 may also facilitate recovery as it weakens the contralesional hemisphere's inhibitory effect on the ipsilesional hemisphere¹²¹. Some studies have used measurements, including clinical assessment, fMRI, motor evoked potentials (MEPs), and central excitatory time, to compare the two types of rTMS and have found no significant differences^{113, 141}. Many studies have demonstrated the positive role of rTMS in functional improvement, although these studies have varied in observation time and stages of stroke^{115, 161}. However, the onset and maintenance time of rTMS remain uncertain.

In this study, we aimed to evaluate the effectiveness of rTMS on motor rehabilitation after stroke using a longitudinal, prospective and randomized study, and to explore the central mechanism of rTMS in motor recovery after ischemic stroke through multimodal functional magnetic resonance imaging.

Methods:

Subjects

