Patients aged 35-80 years, admitted to the Department of Peking Union Medical College Hospital between January 2013 and December 2018 for first onset of acute ischemic stroke will be included in this study. The study will be performed in accordance with the guidelines of the latest version of the Declaration of Helsinki. Subjects will be given written information and a verbal explanation concerning the study prior to obtaining consent for their participation.

Inclusion Criteria

The main inclusion criteria are: 1) stroke patients within 1 week after onset with unilateral cerebral subcortex lesion in the middle cerebral artery territory detected by diffusion weighted image (DWI), 2)

right-handed, 3) without memory loss or intelligence disorder, 4) never suffered stroke before.

Exclusion Criteria

The following patients will be excluded from the study: 1) direct damage to the cerebral cortex, a history of cerebral vessel disease, 2) tendency to hemorrhage or existed brain hemorrhage, 3) epilepsy or other mental disorders, 4) any MRI contraindications.

Grouping and Evaluation

The patients were divided into a real rTMS treatment group and a sham group randomly. A random number was generated by a computer, and the processing method was placed into a sealed envelope. A nurse who was not involved in the clinical evaluation was responsible for issuing and registering the number. The functional scores of the patients were independently assessed by an experienced neurologist at each follow-up time point. The staff members who implemented rTMS were not involved in the clinical assessment, and the rehabilitation physician was not aware of the patient groupings.

The scoring methods included the following: 1) National Institutes of Health Stroke Scale (NIHSS), 2) Barthel Index (BI), 3) Fugl-Meyer Assessment Upper Limb/Lower Limb (FMA-UL/LL), 4) modified Rankin Score (mRS), 5) the resting motor threshold (MT) of the hemiplegic upper limbs. The former 3 scores were the primary endpoints, and the latter 2 scores were the secondary endpoints. We evaluated each patient at 6 time points, including grouping time, the second day after treatment, 1 month after onset, 3 month after onset, 6 month after onset, and 1 year after onset.

rTMS

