The MT (motor threshold) of the ipsilesional and contralesional abductor digiti minimi muscles were determined for every patient before rTMS or sham rTMS to evaluate motor function for both cerebral hemispheres. The RMT was defined as the lowest intensity capable of eliciting at least 5 MEPs of 50 μ V peak-to-peak amplitude in 10 consecutive stimulations when single-pulse TMS was delivered to the contralateral cortex. If the minimum MEP amplitude could not be detected, then it was recorded as 100%. MTs for bilateral cerebral hemisphere were recorded.

All patients received consecutive 10-day rTMS or sham rTMS. We used a Medtronic MagPro type magnetic stimulation device (Medtronic, Minneapolis, MN, USA) and a figure-eight coil (MC-B70, Medtronic). Regarding the safety threshold suggested by the International Federation of Clinical Neurophysiology (IFCN) and related studies, our protocol used 5 Hz rTMS applied to the ipsilesional M1. The treatment involved 50 trains of 20 pulses with 2-second intertrain intervals daily. In the rTMS

treatment group, coils were placed tangent to the scalp, while in the sham group, coils were placed perpendicular to the scalp.

Statistical analysis: Statistical analyses were performed using SPSS version 22.0 (IBM Corp., Armonk, NY, USA). Measurement data are described using means and standard deviations and were compared using the Mann-Whitney *U* test. Enumeration data were compared using the Chi-square test. A *P* value < 0.05 means significant difference.

References:

- [3] Ziemann U. Tms induced plasticity in human cortex. [J] *Reviews in the neurosciences*. 2004;15(4):253-266.

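### The secondary motor threshold endpoint is compared by an unadjusted rank test although both pre-treatment thresholds are on file; the comparison is valid but less precise than it could be

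*Combined protocol and SAP*

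**What the plan says.** The rTMS section of the combined protocol and SAP states: "The MT (motor threshold) of the ipsilesional and contralesional abductor digiti minimi muscles were determined for every patient before rTMS or sham rTMS". The purpose given is "to evaluate motor function for both cerebral hemispheres", and the paragraph ends by confirming that "MTs for bilateral cerebral hemisphere were recorded". It also sets a coding rule: where the minimum response cannot be detected, the threshold is entered as 100%.

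Under Grouping and Evaluation, the last of the five listed measures is "the resting motor threshold (MT) of the hemiplegic upper limbs", and "the latter 2 scores were the secondary endpoints", so MT sits with the mRS below the three primary scales. Grouping time is one of the six assessment points, so a lesion-side baseline is available from that schedule too.

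The Statistical analysis section says that continuous measurements "were compared using the Mann-Whitney *U* test". It names no covariate, change from baseline, ratio or between-side difference, and no sample size or power appears anywhere.

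**The concern.** Follow-up MT on the lesion side reflects at least three things: the person's own level of excitability, the severity of the lesion, and any effect of treatment. A two-sample rank test on the follow-up value leaves the first two in the noise. Both pre-treatment thresholds carry information about them, are collected in every patient, and cannot be affected by treatment. The plan assigns them no part in the comparison they could sharpen.

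What is at stake is precision on one secondary endpoint. Randomisation protects the unadjusted comparison from bias, so the risk is a real difference missed or estimated loosely. With no sample size justification, nothing in the documents shows that precision can be spared.

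**Working it through.** The documents give no SD, correlation, effect size or sample size for MT, so there is no figure of the plan's own to reproduce. Everything below is illustrative and rests on assumed inputs: two-sided 5%, 1:1 allocation, and the values named.

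**Step 1: one baseline covariate.** If a baseline value has correlation r with the follow-up value, adjustment leaves residual variance (1 − r²) of the unadjusted variance. By the normal approximation, 80% power at a standardised effect of 0.5 needs 2 × (1.960 + 0.842)² / 0.5² = 62.8, so 63 per arm unadjusted. Multiplying 62.8 by (1 − r²) and rounding up:

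| r | Residual variance | Needed per arm | Power at 63 per arm |
|---|---|---|---|
| 0 | 1.00 | 63 | 80.1% |
| 0.1 | 0.99 | 63 | 80.5% |
| 0.3 | 0.91 | 58 | 83.7% |
| 0.5 | 0.75 | 48 | 90.0% |
| 0.7 | 0.51 | 33 | 97.6% |

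A lesion-minus-intact difference behaves differently. With equal SDs its variance is 2(1 − r) times the unadjusted one, so it loses precision below r = 0.5 (88 per arm at r = 0.3). Covariate adjustment is the safer form.

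**Step 2: what the intact side adds to the lesion-side baseline.** Let B be the lesion-side baseline, C the intact-side baseline and Y the follow-up. Then R² = (r_YB² + r_YC² − 2 r_YB r_YC r_BC) / (1 − r_BC²). With r_YB = 0.7 and r_YC = r_BC = 0.5, R² = (0.49 + 0.25 − 0.35) / 0.75 = 0.52. Residual variance falls from 0.51 with B alone to 0.48, a further 5.9%. Over the assumed correlations tried (r_YB 0.5 to 0.8, the others 0.3 or 0.5), the further reduction ran from 0.4% to 20.6%.

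**Step 3: power, including the 100% code.** Simulation with 30 per arm and 1,500 replicates per setting:
- Intact-side MT = 50 + person effect (SD 6 or 10) + error (SD 3).
- Follow-up lesion-side MT = 50 + the same person effect + 0.7 × lesion elevation (mean 12, SD 10) + error (SD 6), minus 7 in the active arm, capped at 100.
- Error SD of the lesion-side baseline: 6.
- A share of 0, 20 or 40% undetectable at baseline; 40% of these become detectable at follow-up and the rest stay coded 100.

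The implied Spearman correlation between intact-side and follow-up lesion-side MT is about 0.25 to 0.65. Power in percent:

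| Undetectable | Person SD | Mann-Whitney, follow-up | Rank ANCOVA, intact side | Mann-Whitney, change | Rank ANCOVA, lesion side | Rank ANCOVA, both |
|---|---|---|---|---|---|---|
| 0% | 6 | 63 | 75 | 82 | 92 | 94 |
| 0% | 10 | 50 | 75 | 84 | 90 | 94 |
| 20% | 6 | 44 | 49 | 56 | 71 | 74 |
| 20% | 10 | 34 | 42 | 55 | 58 | 64 |
| 40% | 6 | 26 | 28 | 31 | 42 | 42 |
| 40% | 10 | 20 | 23 | 33 | 33 | 34 |

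The Monte Carlo standard error is at most √(0.5 × 0.5 / 1500) = 1.3 points. From first to last column the gain is 31, 44, 30, 30, 16 and 14 points. The intact side adds 2, 4, 3, 6, 0 and 1 points to the lesion-side baseline.

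**Step 4: the cost of adjusting.** With no treatment effect, rank ANCOVA on the intact side rejected in 3.9% to 5.2% of runs. In a separate simulation (63 per arm, effect 0.5) with the two sides uncorrelated, that adjustment moved power from 78.2% to 77.7% with none at the 100% code, 40.7% to 39.9% with 20% there, and 18.6% to 18.3% with 40% there.

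**The case against.** The strongest reply is that nothing here is an error. The planned test is valid, the endpoint is secondary, and every input to the size of the gain is assumed. The simulation also builds in a benefit by giving both sides the same person effect. All of that stands, and it is why the point is an optional improvement.

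A second reply is that the plan does not say whether follow-up values or changes are compared. If changes were meant, the lesion-side baseline would already be in use. On the table above, the step from a Mann-Whitney test on change to the two-covariate model is 12, 10, 18, 9, 11 and 1 points: smaller than from the raw comparison, and close to nothing in one setting. But the text mentions no change score, so this is at best left open.

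Third, a reader might infer that the intact side is the natural reference and that its omission is the main loss. The figures do not support that. In all six settings, adjusting for the intact side alone has less power than an unadjusted test on change, and the lesion-side baseline is generally the more informative covariate. Nor is the intact-side value plainly discarded: the plan gives a purpose for measuring it, and the general rule for continuous data could cover an arm comparison of it. That rule does not cover its use to sharpen the lesion-side comparison.

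**Conclusion.** The point holds as a missed gain in precision on one secondary endpoint. Two pre-treatment thresholds are recorded in every patient, and the stated analysis of hemiplegic-side MT uses neither. On the assumed inputs, adjusting for both raises power by 14 to 44 points over the test as written. Most of that comes from the lesion side; the intact side adds about 0 to 6. The gain shrinks as more patients carry the 100% code, and could be slight if the true correlations are low (1% of variance at r = 0.1).

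Three stronger readings should be resisted:
- That MT carries the mechanism question. The Background section assigns that aim to multimodal fMRI.
- That the adjustment would examine inhibition between the hemispheres. The Background remark that "it weakens the contralesional hemisphere's inhibitory effect on the ipsilesional hemisphere" concerns low-frequency stimulation of the contralesional side, whereas this trial stimulates the ipsilesional side at 5 Hz. A pre-treatment covariate would not test that mechanism in any case.
- That the gain is free and certain. No new data are required, but an improvement is not guaranteed.

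**What to change.** Add to the Statistical analysis section that hemiplegic-side MT at each follow-up visit where it is compared will be analysed by a rank-based ANCOVA on treatment arm. Pre-treatment lesion-side MT is the main covariate and pre-treatment intact-side MT an additional one. Specify that:
- only pre-treatment values serve as covariates, since later intact-side values could themselves respond to treatment;
- one named baseline measurement is used, if the grouping-time and pre-stimulation thresholds are separate readings;
- values coded 100% enter as ties at the top rank, with their number reported by arm and visit;
- the unadjusted Mann-Whitney test is kept as a sensitivity analysis.

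The cost is a few sentences, one extra model in the software already named, and two degrees of freedom. No additional measurement is needed.

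### The primary scores are measured at baseline, but the arms are compared by an unadjusted Mann-Whitney test; the test is valid, yet precision is lost if baseline predicts outcome

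*Combined protocol and SAP*

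**What the plan says.** The Grouping and Evaluation section of the combined protocol and SAP lists five measures: NIHSS, Barthel Index, Fugl-Meyer upper/lower limb, mRS and motor threshold. It then ranks them: "The former 3 scores were the primary endpoints, and the latter 2 scores were the secondary endpoints". On timing it says "We evaluated each patient at 6 time points, including grouping time". The five later visits run from the second day after treatment to one year after onset. A baseline value of each primary score therefore exists by design.

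Allocation is random ("The patients were divided into a real rTMS treatment group and a sham group randomly"), and no stratification by severity is described.

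The Statistical analysis section is one short paragraph. For scores it says "Measurement data are described using means and standard deviations and were compared using the Mann-Whitney" test. For counts it says "Enumeration data were compared using the Chi-square test". The criterion is a P "value < 0.05 means significant difference". It names no covariate, regression, analysis of covariance, repeated-measures model or change-score definition, and nothing elsewhere in the document supplies one.

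**The concern.** A patient's deficit in the first week after stroke may well predict the deficit at later visits. If it does, part of the spread in the follow-up score is already explained by a number the trial holds. A test that ignores that number treats the explained spread as noise, so a real effect of rTMS is more likely to be missed and the effect is estimated less precisely than the data allow.

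The wording also does not say whether the raw follow-up score or the change since grouping enters the test. Change scores do use baseline, but they fix its coefficient at 1, which can be worse than ignoring it.

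**Working it through.** **Inputs from the document.** Two randomised arms; significance at 0.05 (sidedness not stated); Mann-Whitney for scores; baseline measured for each primary score. There is no sample size, power, SD, effect size or correlation, so there is no planned figure to reproduce.

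**Assumptions.** Two-sided 0.05, equal arms, a 0.5 SD effect, and bivariate normal baseline and outcome with equal variances and correlation ρ.

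**1. Sample-size arithmetic (linear approximation, 80% power).** With n per arm = 2(1.960 + 0.842)² × V / 0.5² ≈ 62.8 × V, rounded up, and V the variance factor:

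| ρ | Raw score, V = 1 | Adjusted, V = 1 − ρ² | Change score, V = 2(1 − ρ) |
|---|---|---|---|
| 0 | 63 | 63 | 126 |
| 0.3 | 63 | 58 (V = 0.91) | 88 |
| 0.5 | 63 | 48 (V = 0.75) | 63 |
| 0.7 | 63 | 33 (V = 0.51) | 38 |
| 0.8 | 63 | 23 (V = 0.36) | 26 |

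The unadjusted comparison needs 63/58 = 1.09, 63/48 = 1.31 and 63/33 = 1.91 times as many patients at ρ = 0.3, 0.5 and 0.7. Change scores match raw scores where 2(1 − ρ) = 1, that is at ρ = 0.5, and are worse below it.

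**2. Simulated power of the rank tests** (20,000 trials per cell, Monte Carlo standard error at most about 0.0035). Quade's method ranks outcome and baseline over both arms, regresses outcome ranks on baseline ranks, and compares the residuals between arms.

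| Setting | Test | ρ = 0 | 0.3 | 0.5 | 0.7 | 0.8 |
|---|---|---|---|---|---|---|
| 20/arm | Mann-Whitney, raw | 32–33% at every ρ | | | | |
| | Quade | 32% | 34% | 40% | 52% | 64% |
| 30/arm | Mann-Whitney, raw | about 46% at every ρ | | | | |
| | Mann-Whitney, change | 26% | 34% | 46% | 67% | 84% |
| | Quade | 46% | 48% | 55% | 71% | 84% |
| 50/arm | Mann-Whitney, raw | 67–68% at every ρ | | | | |
| | Quade | 67% | 71% | 78% | 90% | 97% |

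At 30 per arm Quade gives 45%, 47% and 51% at ρ = 0.1, 0.2 and 0.4. At ρ = 0.9 change scores reach 98.5% against 97.4% for Quade.

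**3. Ceiling case, 30 per arm.** Bounded scales can pile up at their best value. Here 30% of sham patients are at the ceiling, mean recovery is 1 SD before capping, scores move in 0.2 SD steps, and ρ is measured before capping. At ρ = 0, 0.3, 0.5, 0.7 and 0.8, raw Mann-Whitney gives 41–42% throughout, change scores 17%, 21%, 27%, 35% and 46%, and Quade 41%, 44%, 51%, 62% and 75%. Change scores overtake raw scores only at about ρ = 0.77 (40.1% against 41.6% at 0.75; 42.8% against 41.9% at 0.78).

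**4. Type I error.** With no effect, the raw, change, Quade and linear ANCOVA tests rejected in 4.6% to 5.5% of trials at 20, 30 and 50 per arm and in the ceiling case. The planned test is valid.

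**5. Interval width.** At 30 per arm the 95% interval for the mean difference from linear ANCOVA is 0.96, 0.87, 0.72 and 0.61 times the width of an unadjusted t interval at ρ = 0.3, 0.5, 0.7 and 0.8. This is close to √(1 − ρ²) = 0.95, 0.87, 0.71 and 0.60. At ρ = 0 to 0.1 the ratio is 1.00 to 1.01. In the ceiling case the ratios are 0.97, 0.90, 0.77 and 0.68, with coverage of 94.7% to 95.2%.

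**The case against.** The strongest reply is that this is a choice between two valid tests. The planned test controls its error rate, and nothing in the document becomes biased or unanalysable because of it. The gain at ρ = 0.3 is about two percentage points of power at 30 per arm. The larger gains need ρ of about 0.5 or more, which the document does not establish, and the correlation may differ across scores and visits. That is right, and it is why the point is about efficiency and why its size is given as a range.

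The plan may also intend change scores, in which case baseline is used. The text does not say so. If it were so, the planned test would be weaker than the raw comparison below ρ = 0.5. With normal scores and ρ of 0.8 or more, however, change scores match or slightly beat Quade, so the advantage of adjustment over change scores is not universal. The 0.77 crossover belongs to the particular ceiling scenario and is not a general constant.

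The plan reports no confidence interval at all. The width ratios therefore describe what an added estimate would gain, not a flaw in one already planned.

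Finally, parts of the document are in the past tense. If outcomes by arm have been seen, changing the primary test is a post hoc decision. This limits how the fix may be presented but does not remove the reason for it.

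**Conclusion.** The point holds. The plan collects a baseline for every primary score and makes no stated use of it in the between-arm comparison. The unadjusted Mann-Whitney test is valid under randomisation; what may be lost is precision. Under the assumed 30 per arm and 0.5 SD effect, the power forgone relative to Quade is nil at correlations of 0 to 0.1, about 2 points at 0.3, 9 at 0.5, 25 at 0.7 and 38 at 0.8. The pattern is similar at 20 and 50 per arm and persists with a ceiling. All of these inputs are assumptions, so the direction is firm and the size is not. The change is worth making because it is cheap and, in the settings examined, costs essentially nothing when baseline is uninformative.

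**What to change.** 1. State which value is analysed (the score at the visit) and name one primary visit, so that the adjusted comparison is fully defined.
2. At that visit, compare each primary score between arms by Quade's rank analysis of covariance, adjusted for the same score at grouping time. With two arms, the residuals can be compared by a two-sample t test.
3. Keep the unadjusted Mann-Whitney test as a sensitivity analysis.
4. Report a baseline-adjusted mean difference with 95% confidence interval from a linear model of the score on arm and the same score at grouping time. State in advance that the P value comes from the rank analysis, since the two can disagree.
5. Say how a missing baseline or visit score is handled in this analysis.
6. Date the change before outcomes by arm are seen. If they have been seen, report the adjusted analysis with a clear statement of when it was specified.

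The cost is SAP wording and slightly more analysis, using only ranking, linear regression and a comparison of residuals. No new data, patients or visits are needed. The trade-offs are that Quade's method gives a P value but no effect estimate, hence the second model, and that the gain is small at correlations of 0.2 to 0.4. Error control across the primary scores and the visits is a separate matter that this change does not settle.

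### Each patient is scored at five post-baseline visits over a year, but the plan specifies no analysis of how the arm difference changes over time and no method that uses the repeated scores together.

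*Combined protocol and SAP*

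**What the plan says.** The last paragraph of the Background gives the aim: "we aimed to evaluate the effectiveness of rTMS on motor rehabilitation after stroke using a longitudinal, prospective and randomized study", with a second, exploratory aim about mechanism. Just before it, the Background names the open question in the literature: "the onset and maintenance time of rTMS remain uncertain".

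Under Grouping and Evaluation the schedule reads "We evaluated each patient at 6 time points, including grouping time, the second day after treatment, 1 month after onset", followed by "3 month after onset, 6 month after onset, and 1 year after onset". That is one baseline score and five later ones. NIHSS, BI and FMA-UL/LL come first in the list of scores, and the section says "The former 3 scores were the primary endpoints, and the latter 2 scores were the secondary endpoints".

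The Statistical analysis section is one short paragraph. For the scores it says "Measurement data are described using means and standard deviations and were compared using the Mann-Whitney" U test. It adds a Chi-square test for counts and a 0.05 significance threshold. It names no primary visit, does not say whether raw scores or changes are compared, and includes no per-patient summary, repeated-measures method, baseline adjustment or arm-by-visit contrast.

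**The concern.** A Mann-Whitney test compares two groups on one value per patient, and the plan does not say which value that is when each patient has five post-baseline scores. The most natural reading is a separate test at each visit. A reader of the results would then judge when the effect starts, and whether it lasts, from the visits that cross 0.05. That inference fails: significance at one visit and not at another does not show that the effect differs between them. A constant benefit could be reported as delayed or fading, and no specified analysis would show that a real fade had occurred.

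This is separate from multiplicity. Naming one primary visit or adjusting the level would still leave the change in the arm difference unexamined and the other visits unused.

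**Working it through.** **Inputs from the documents.** Six assessments per patient, so five after baseline; two arms; threshold 0.05. No sample size, power, effect size, SD or between-visit correlation is stated, so there is no planned figure to reproduce.

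**Assumed inputs.** 20, 30 or 60 patients per arm; normally distributed scores; the same 0.5 SD effect at all five visits; between-visit correlation r from 0.5 to 0.85; Mann-Whitney at 0.05 on each visit; 3,000 simulated trials per setting.

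**Step 1. Reading the time course from visit-by-visit P values when the true effect is constant.**

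| Result | Share of trials |
|---|---|
| Some visits significant, others not | about 30–70% |
| Significant at the first post-treatment visit, not at 1 year (false fade) | about 7–17% |
| The reverse (false late onset) | 7–19% |
| Direct test of the within-patient change, 1 year minus first post-treatment visit, wrongly significant | 4–6% |

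**Step 2. What a single test at 1 year can show.** If the effect has faded to zero by then, the 1-year Mann-Whitney rejects in 4–6% of trials. If 0.5 SD persists, it rejects in 32–79% (20 to 60 per arm). It is therefore a valid test of whether a difference is present at 1 year, but it does not test whether the difference has changed.

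**Step 3. Precision of the change contrast.** The variance of the last-minus-first difference, relative to one visit, is 2(1 − r):
- r = 0.5: 2 × 0.5 = 1.00
- r = 0.7: 2 × 0.3 = 0.60
- r = 0.85: 2 × 0.15 = 0.30

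At r = 0.5 a complete fade from 0.5 SD to zero is therefore no easier to detect than a 0.5 SD effect at one visit. Simulated power is about 31% with 20 per arm and 44% with 30 per arm. With a larger initial effect of 0.6 SD and 30 per arm, power to detect a complete fade is 0.61, 0.82 and 1.00 at r = 0.5, 0.7 and 0.9.

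**Step 4. Using the five scores together.** The variance of a five-visit mean, relative to one visit, is (1 + 4r)/5:
- r = 0.5: 3.0/5 = 0.60
- r = 0.7: 3.8/5 = 0.76
- r = 0.85: 4.4/5 = 0.88

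With a constant 0.5 SD effect, power rises from about 45% to 56% (30 per arm, r = 0.7) and from about 76% to 93% (60 per arm, r = 0.5). At r = 0.85 the gain is small: about 44% to 49% with 30 per arm. If the effect instead fades linearly to zero, the mean has 18% power against about 46% for the first visit alone (30 per arm, r = 0.7). Averaging helps only when the effect is roughly constant.

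**The case against.** The plan is silent on how the visits are used; it does not commit to visit-by-visit testing. Mann-Whitney is not the obstacle either, since it can be applied to a per-patient change or mean. This stands: the gap is the unspecified quantity and contrast, not the choice of test.

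Three stronger readings are tempting, and the documents do not support them.

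- A reader might infer that persistence is never tested. A Mann-Whitney comparison at the scheduled 1-year visit would be a valid test of a difference at that time (step 2). The plan does not specify such a comparison, but nothing rules it out. What is missing is any test of change in the effect.
- A reader might infer that Mann-Whitney is the only planned test. Chi-square is planned as well, though it also takes one value per patient.
- A reader might infer that lasting benefit is a stated aim. The aim is effectiveness. Maintenance appears as a gap in the Background, and its relevance here is inferred from that and from the year of follow-up.

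A contrast of change also has limits. Step 3 shows that in a small trial it can miss even a complete fade, so a non-significant result does not demonstrate maintenance. NIHSS, BI and FMA are bounded, and a ceiling can shrink late differences and look like fading. These points affect how the contrast is reported and read; they do not remove the need for it.

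**Conclusion.** The concern holds in this form: a design described as longitudinal, with five post-baseline scores per patient, has no specified contrast of the arm difference between visits and no method that uses those scores together. If time-course conclusions were drawn from visit-level significance, roughly one trial in 14 to one in 6 (7–17%) would show a false fade under a constant effect. That figure rests on the assumed 0.5 SD effect, 20 to 60 per arm, r of 0.5 to 0.85 and normal scores, none of which the plan states. The logical point does not depend on them.

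This should be corrected, but it does not invalidate the trial, because a comparison at any single visit remains sound. Lost power is not a firm part of the case, since the gain from averaging depends on the shape of the effect.

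**What to change.** For each primary score, add one pre-specified longitudinal analysis to the Statistical analysis section. The preferred form is a repeated-measures model with arm, visit, arm-by-visit and baseline score, allowing for correlation within patient. Report the arm difference with a 95% confidence interval at each post-baseline visit, and for 1 year minus the first post-treatment visit.

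A simpler alternative is to compare the per-patient change between those two visits by Mann-Whitney, with a Hodges-Lehmann interval. The two are not equivalent: they differ in what they estimate, in distributional assumptions and in handling of missed visits. One should be chosen in advance.

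State three rules of interpretation:
- a claim that the effect changed over time rests on the change contrast;
- a claim of lasting benefit rests on the 1-year difference and its interval;
- a non-significant change contrast is not evidence of maintenance.

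The cost is a few sentences of plan text and some added analysis, with no new visits or patients. The downside is that the change contrast will be imprecise in a small trial, so its interval may settle little. Score distributions at late visits should be shown so that ceiling effects can be recognised.
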